22.8 SECONDARY EFFECTIVENESS ENDPOINTS

Secondary effectiveness endpoints will be analyzed descriptively.

For continuous variables (CONT), results will be summarized with the numbers of observations, means, standard deviation, median, minimums and maximums. Differences between the two groups, where specified, will be summarized with the differences of the two means, and 95% confidence intervals for the difference between the means. These calculations will be done under the assumption that data for the two groups are independent and approximately normally distributed. The confidence interval for the difference of two means will be calculated under the assumption of unequal variances. If the asymptotic assumptions fail, then nonparametric summary statistics (medians, 25th and 75th percentile) may be displayed as an alternative.

For binary variables (BIN), results will be summarized with patient counts, percentages/rates. Differences between the two groups, where specified, will be summarized with the difference in percent and the Newcombe score 95% confidence interval for the difference of two percentages.

For correlation analysis, Spearman correlation will be used to assess the association between two continuous variables. The correlation coefficient and the 95% confidence intervals will be reported.

CONFIDENTIAL Page **61** of **69**

There are three secondary endpoints controlled multiplicity (see below):

- The mean change in points for MADRS score from baseline to Week 10. This will be evaluated using the same statistical methodology as the primary endpoint.
- Clinical Response will be analyzed as a responder endpoint. Clinical Response is defined as a >50% reduction from the baseline HDRS-17 or MADRS score, MADRS-s at Week 10.
- Remission will be analyzed as a responder endpoint where remission is defined as an HDRS-17 score ≤7 or a MADRS score ≤10). The endpoint will be tested using a two-group large-sample normal approximation test of proportions with a one-sided 0.025 considered significant.
- Quality of life improvement as measured by EQ-5D-3L in the active compared to sham arm at week 10 compared to baseline.

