6 STUDY SUMMARY

Study Full Title	Transcranial Direct Current Stimulation in Major Depressive Disorder: A Double-blind, Placebo-controlled, Randomized, Superiority Trial	
Study Sponsor	Flow Neuroscience AB	
Study Number	FL001	
Device Name	Flow FL-100	
Protocol Date	10Jan2023	
STUDY OVERVIEW		
Study Design	Double-blind, placebo-controlled, randomized, superiority, remote.	
Purpose	The purpose of this trial is to investigate the use of the Flow FL-100 device at-home to treat Unipolar Major Depressive Disorder (MDD) in a double-blind RCT.	
Expected Study Duration	10 months	
Evaluation Schedule	Participants will undergo evaluations at the following study visits. Various evaluations regarding depression severity, suicidal ideation will be performed (see Schedule of Evaluations for more detail): • Pre-Treatment Phase - Week -3 - Week -2 - Week -2 - Week -1 • Blinded Phase - Week 0 - Week 1 - Week 4 - Week 7 - Week 10 • Open-Label Phase - Week 20 At week 0, 1, 4, 7, 10, 20, participants will also complete the MADRS-s on their personal smartphone or other device running Android 5.0+ or iPhone Operating System (iOS) 12+.	
ELIGIBILITY CRITERIA		

Intended Participant	Up to 270 participants will be randomized at 2 sites, one located in the United Kingdom and the other in the United
Intended Participant Population	States. The recruitment will be capped to 155 for each of the sites.
	Siles.
	1:1 randomization: Flow FL-100 vs. Sham
	To be eligible to participate in this study, participants must meet all the following criteria:
	1. Be ≥18 years.
	2. Have a diagnosis of Unipolar MDD with a current
	depressive episode as defined by the diagnostic
	criteria in the Diagnostic and statistical manual of
	mental disorders – 5th edition (DSM-V) 3. Have a Hamilton Depression Rating Score (HDRS-17)
	of \geq 16.
	4. For 6 weeks prior to enrollment, are either:
	a. not taking antidepressant medication or:
	b. are taking a stable antidepressant regimen
	with a stable medication source and agree to
	continue the same regimen throughout study participation.
Diagnosis and Inclusion	5. If in psychotherapy, have maintained stable
Criteria	psychotherapy for at least 6 weeks prior to enrollment.
	6. Have access to a stable internet connection through
	which the treatment will be received.
	7. Have access to a smartphone or other device running
	Android 5.0+ or iPhone Operating System (iOS) 12+
	(e.g., reasonably new iPhone/iPad or Android phone),

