11.6 SECONDARY ENDPOINTS

- Arm difference in HDRS-17 response and remission rate at week 10.
- Arm difference in MADRS average score change, and response and remission rate at week 10.
- Arm difference in MADRS-s average score change, and response and remission rate at week 10.
- Quality of life improvement as measured by EQ-5D-3L in the active compared to sham arm at week 10.

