22.2 SAMPLE SIZE ASSUMPTIONS AND CALCULATIONS

The sample size calculation is based on data from Brunoni et al (2017). The calculation is based on a two- sample t-test for mean difference with the following assumptions:

- Group difference in means = 3.2
- Standard deviation of Investigational and Sham groups = 7.1 and 7.9, respectively
- One-sided type I error = 0.025
- 80% power

The resulting sample size is 176 subjects. To obtain an increase in statistical power (87.6%), 216 subjects were chosen. Accounting for 20% attrition, the overall sample size will be 270 subjects.

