22.5.1 MULTIPLE IMPUTATION ANALYSIS

The mixed model for repeated measures (MMRM) allows for inclusion of patients with missing Week 10 values. If all subjects have at least one follow-up evaluation, the following MMRM will be utilized for the primary superiority test. If there are subjects without at least one post baseline assessment, the multiple imputation analysis summarized below will be the primary analysis method. Least squares estimated values from the MMRM will be reported for HDRS-17 at each visit and as such these estimates include implicit imputations of missing values.

Details of the MMRM used to evaluate the primary endpoint are described in the attached Statistical analysis plan.

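### MADRS-s mean change at week 10 is assigned an unadjusted difference of two means while MADRS change gets the primary repeated-measures model, which costs precision and some robustness to drop-out

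*Protocol*

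**What the plan says.** Section 11.6 of the protocol lists "Arm difference in MADRS-s average score change, and response and remission rate at week 10", next to a parallel entry for MADRS. On timing, section 6 states: "At week 0, 1, 4, 7, 10, 20, participants will also complete the MADRS-s on their personal smartphone". Table 1 in section 7 puts HDRS-17 and MADRS at the same post-baseline visits (weeks 1, 4, 7 and 10).

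Section 22.8 opens with a general rule: "Secondary effectiveness endpoints will be analyzed descriptively". For continuous variables it then specifies "Differences between the two groups, where specified, will be summarized with the differences of the two means, and 95% confidence intervals" and adds: "The confidence interval for the difference of two means will be calculated under the assumption of unequal variances". It names no baseline covariate and no earlier visit. MADRS mean change is taken out of this default: "This will be evaluated using the same statistical methodology as the primary endpoint". Under 22.5 and 22.5.1 that means the MMRM, with multiple imputation as the primary method if any subject has no post-baseline assessment. Section 22.5.1 gives the reason for the model: "The mixed model for repeated measures (MMRM) allows for inclusion of patients with missing Week 10 values".

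MADRS-s mean change is not among the endpoints taken out, and section 22.9 again tags MADRS-s as a continuous variable to be summarised by data type. Section 22.6 leaves missing-data handling to the SAP. Section 15.6 says data already collected from withdrawn or lost participants enter the analysis.

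**The concern.** The clinician-rated and self-rated versions of one scale, measured at the same visits, get different estimators, and no reason is given. The protocol names the estimator here, so this is not simply a detail left to the SAP.

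Two things are at stake. The first is precision, because a raw difference ignores the baseline score and three intermediate visits. The second is robustness. The plan expects appreciable loss ("Accounting for 20% attrition, the overall sample size will be 270 subjects"). Section 15.2 withdraws participants after a 30% rise in HDRS-17, section 15.4 withdraws those who cannot reach 22 of 36 sessions, and the early termination visit is optional. Completely random missingness at week 10 is therefore hard to assume. Anyone setting the MADRS and MADRS-s treatment effects side by side would also see differences due partly to method and not only to rater.

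**Working it through.** **1. The plan's own figures (section 22.2; HDRS-17).** Inputs: difference 3.2, SDs 7.1 and 7.9, one-sided 0.025, 80% power.
- Common SD = √((7.1² + 7.9²)/2) = √56.41 = 7.51.
- n per arm = 2 × 56.41 × (1.960 + 0.842)² / 3.2² ≈ 86.5, so 87 per arm, or 174 against the stated 176. Power at 176 by the t distribution is 80.2%.
- Power at 216 is 87.6%, as stated. 216/0.80 = 270, as stated.

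The protocol gives no effect, SD or correlation for MADRS-s. HDRS-17 values stand in for them below, and every MADRS-s figure is an assumption.

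**2. What losing 20% costs a raw difference.**
- 216 with a week-10 value: SE = 7.51 × √(2/108) = 1.02.
- All 270: SE = 7.51 × √(2/135) = 0.91.
- Ratio √(135/108) = 1.12. For a difference of 3.2, power is 87.6% against 93.7%.

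**3. What ignoring baseline costs.** With equal variances σ² and baseline-to-week-10 correlation ρ, a change score has variance 2σ²(1−ρ) and a baseline-adjusted score σ²(1−ρ²). The ratio is (1+ρ)/2: 0.65 at ρ = 0.3, 0.70 at 0.4 and 0.75 at 0.5. Much of the gain therefore exists without any drop-out.

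**4. Main simulation.** 135 per arm, true difference −3.2, change SD 7.5, 1,500 runs per setting, monotone drop-out after weeks 1, 4 and 7 with about 15-20% lost by week 10. Correlations were 0.3-0.5 between baseline and later visits and 0.5-0.8 among later visits. The raw difference in observed change is compared with a likelihood-type estimate using all visits and adjusting for baseline. Drop-out, where it depends on outcome, depends on change from baseline.

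| Drop-out mechanism | Raw difference | Repeated measures | SE raw | SE repeated measures | Variance ratio |
|---|---|---|---|---|---|
| Completely at random | −3.17 to −3.19 | −3.18 to −3.20 | 1.01-1.02 | 0.78-0.84 | 0.60-0.68 |
| Worse patients leave, same rule in both arms | −3.06 to −3.11 | −3.18 to −3.21 | 0.94-0.98 | 0.79-0.81 | 0.66-0.76 |
| Depends on worsening in sham only | −2.27 to −2.42 | −3.17 to −3.20 | 0.97-1.01 | 0.80-0.83 | 0.67-0.70 |
| Opposite directions in the two arms | −1.49 to −1.76 | −3.17 to −3.22 | 0.97-1.00 | 0.78-0.84 | 0.65-0.75 |

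Bias of the raw difference, down the rows: about 0; 0.09-0.14; 0.78-0.93; 1.44-1.71 points, all towards zero. Every mechanism was missing completely at random or missing at random, the conditions under which the repeated-measures estimate is expected to hold.

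**5. Simulations of the withdrawal rule itself (true effect −3.4).**
- 30% rise applied to the simulated score as a stand-in for HDRS-17, with or without 3.5% random loss per visit (19-32% missing): raw −3.0 to −3.1, repeated measures −3.3 to −3.5. Raw variance is 16-27% larger, and 42% larger with nothing missing.
- 30% rise applied to a correlated HDRS-17 (cross-scale correlation 0.5-0.7, within-scale 0.4-0.6), which is closer to section 15.2: raw −3.10 to −3.28. That is 0.12-0.30 points too small (4-9%), with about 9-15% removed by the rule.

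**6. A less adverse setting.** With AR(1) correlation and drop-out driven by the last score level instead of change from baseline, bias was at most about 0.06 even with opposite mechanisms by arm. Where the raw SE was near the plan's (about 1.0), the variance ratio was 0.69-0.72. At lower correlations it fell to 0.51, but there the raw SE reached 1.2-1.5, so those settings are not used for the size.

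**7. Range for precision.** Step 4 gives 24-40% lower variance (ratios 0.76 to 0.60). In step 5, 1/1.16 = 0.86, 1/1.27 = 0.79 and 1/1.42 = 0.70 give 14%, 21% and 30% lower. Together: roughly 15-40%.

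**The case against.** A reader might infer that drop-outs are discarded. The protocol does not say so. Section 22.6 defers missing data to the SAP, section 15.6 keeps earlier data in the analysis, and an early termination visit can collect MADRS-s. What can be said is narrower: a week-10 difference of observed means, taken as written, makes no use of someone who has no week-10 value.

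A reader might also infer that the estimate is biased. That is conditional. The section 15.2 rule is the same in both arms, although it may trigger more often in sham. When modelled on HDRS-17 it costs 0.1-0.3 points, towards zero and well inside a standard error near 1. The larger figures need mechanisms that differ by arm.

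Nor does the choice of estimator undermine the planned comparison of the two scales. Sections 22.8 and 22.9 make that a Spearman correlation between MADRS and MADRS-s, which does not depend on how the arm difference is estimated.

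Finally, the two endpoints do not have equal standing throughout. MADRS mean change is in the multiplicity-controlled list of 22.8 and MADRS-s mean change is not. Reserving a model for controlled endpoints is a common choice, and much of the precision gain comes from baseline adjustment, not from recovering drop-outs. All of this stands and lowers the priority. It does not remove the point, because 22.8 states a less efficient estimator for a named endpoint when a better one is already planned for its sister scale.

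**Conclusion.** The point holds as a free improvement of low priority. Section 22.8 puts MADRS-s mean change under an unadjusted two-mean comparison, and the precision loss appeared in every setting tried: the repeated-measures alternative has roughly 15-40% lower variance. Bias towards zero is possible but not established, and ranges from about nil to about 1.7 points depending on an unknown drop-out mechanism. The sizes rest on assumed MADRS-s effects, SDs, correlations and drop-out mechanisms. The primary result and the multiplicity-controlled tests do not change. The benefit is a more precise and more robust secondary estimate, comparable in method with the MADRS estimate.

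**What to change.** Add one sentence to section 22.8: MADRS-s mean change at week 10 is analysed with the same baseline-adjusted MMRM (weeks 1, 4, 7 and 10) and the same missing-data rules as HDRS-17 and MADRS. Table 1 shows MADRS-s both before treatment and at week 0, so the sentence should name which score is the baseline covariate. Keep the raw means and their difference as descriptive output, and align the SAP. If the SAP already specifies this model, only the protocol text needs correcting.

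The cost is one sentence and one further run of a model already planned for MADRS, with no extra data, visits or participants.

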22.4 RANDOMIZATION

After a subject has met all inclusion criteria and none of the exclusion criteria, and creates an account in the Flow app, the subject will be randomized. Randomization will be performed in a 1:1 ratio to the Active and Sham groups. Randomization will be performed using randomly permuted block sizes of 4 and 6 and done independently for the two sites.

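### The remission test omits baseline severity and site: it is valid, but adjusting for them is a cheap way to gain a little power

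*Protocol*

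**What the plan says.** Section 22.8 names the remission test outright: "The endpoint will be tested using a two-group large-sample normal approximation test of proportions", "with a one-sided 0.025 considered significant". The definition given there is that "remission is defined as an HDRS-17 score ≤7 or a MADRS score ≤10". For binary variables in general, the section reports "the difference in percent and the Newcombe score 95% confidence interval for the difference of two percentages", which is also unadjusted. No covariate or stratum is attached to either.

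Other parts of the protocol bear on this:
- **Allocation (22.4).** "Randomization will be performed in a 1:1 ratio to the Active and Sham groups", and "Randomization will be performed using randomly permuted block sizes of 4 and 6 and done independently for the two sites". Site is therefore a randomisation stratum.
- **Baseline data (Table 1 and 13.1).** HDRS-17 and MADRS are both rated at the screening and baseline call.
- **Primary endpoint (11.5, 22.5).** This is an adjusted mean difference from a mixed model for repeated measures. For MADRS mean change, 22.8 says: "This will be evaluated using the same statistical methodology as the primary endpoint".
- **Covariates (22.7).** Baseline variables serve only to define subgroups for the primary endpoint.
- **Multiplicity (22.10).** Secondary endpoints are tested only after the primary succeeds. Clinical response comes first, then the remaining endpoints under Hochberg.

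Sections 22.5.1, 22.6 and 22.10 hand details to the SAP. Section 22.8 does not do so for the remission test.

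**The concern.** Remission is a fixed cut-off on the final score, while entry requires HDRS-17 of at least 16 with no upper limit (12.2). A participant who enters at 16 must fall 9 points to reach 7; one who enters at 26 must fall 19. If the starting score predicts who gets below the cut-off, a test that ignores it leaves explainable variation in the standard error. The protocol itself treats this variable as informative: Section 22.13 lists baseline scores among the case-mix factors that might explain a difference between sites.

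What is at stake is a few points of power on a secondary endpoint that carries alpha. The two continuous depression endpoints are described as adjusted, and the stated remission test is not.

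**Working it through.** **1. The plan's own figures.** The pooled SD is √((7.1² + 7.9²)/2) = √56.41 = 7.511. For a 3.2-point difference at one-sided 0.025, the two-sample t-test gives 79.8% power with 87 per arm and 80.2% with 88 per arm, so 176 in total. With 108 per arm the power is 87.6%. Attrition: 216/(1 − 0.20) = 270. All figures in 22.2 reproduce. The protocol gives no power for remission.

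**2. Inputs for remission.**
- From the protocol: 3.2-point effect, 216 or 270 participants, one-sided 0.025, 1:1 allocation in blocks of 4 and 6 within two sites, baseline HDRS-17 ≥16, remission HDRS-17 ≤7.
- Assumed: remission of about 20% on sham and 33% on active, a baseline to Week 10 correlation ρ from 0 to 0.5, a site difference of 0 or 2 points, and complete data. The protocol gives no sham remission rate and no correlation.

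**3. Hand check of the unadjusted power.** Take p₀ = 0.194, p₁ = 0.329 and 108 per arm (the simulated rates at ρ = 0):
- pooled rate 0.2615; null SE = √(0.2615 × 0.7385 × 2/108) = 0.0598
- alternative SE = √((0.194 × 0.806 + 0.329 × 0.671)/108) = 0.0591
- power = Φ((0.135 − 1.96 × 0.0598)/0.0591) = Φ(0.30) ≈ 62%

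The simulation gives 62.9%, with a Monte Carlo standard error of √(0.64 × 0.36/3000) ≈ 0.9 points.

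**4. Simulation.** There were 3,000 trials per setting. Three analyses were compared: the planned test, a Cochran–Mantel–Haenszel test stratified by site, and a logistic model on arm, site and baseline HDRS-17 standardised to a risk difference with an influence-function standard error. Results for N = 216 with no site difference:

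| ρ | Planned test | Site-stratified | Adjusted | Variance ratio, adjusted/planned |
|---|---|---|---|---|
| 0 | 62.9% | 62.2% | 63.5% | 1.01 |
| 0.2 | 63.7% | 63.3% | 65.1% | 0.98 |
| 0.3 | 64.7% | 64.3% | 66.9% | 0.955 |
| 0.4 | 64.6% | 64.1% | 68.6% | 0.922 |
| 0.5 | 64.4% | 64.1% | 71.5% | 0.867 |

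The equivalent extra sample is 216/ratio − 216: about 4, 10, 18 and 33 participants for ρ = 0.2, 0.3, 0.4 and 0.5, and none at ρ = 0. With N = 270, power moves from 72–74% to 74–80%, and the largest gain is 80.2 − 73.6 = 6.6 points.

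**5. Site against baseline.** With a 2-point site difference and N = 216, planned against site-stratified power is 62.2/61.8, 63.6/63.7, 61.4/61.7, 63.6/63.6 and 63.4/63.5% for ρ = 0, 0.2, 0.3, 0.4 and 0.5. Site alone moves power by less than 1 point in every setting.

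**6. Validity.** Under no effect (10,000 trials per setting, four settings), one-sided type I error is 0.023–0.025 for the planned test and 0.024–0.027 for the adjusted one. The Monte Carlo standard error is about 0.0016.

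**7. Gatekeeping.** In further runs (2,000 trials per setting, N = 216, assumed remission of about 22% and 35%), the quantity of interest was the chance of passing primary, response and remission, each at 0.025 and without the Hochberg step. It was 0.46 with either remission test at ρ = 0. Adjusting remission raised it from 0.47 to 0.49 at ρ = 0.2–0.3 and from 0.49 to 0.53 at ρ = 0.5. Stand-alone unadjusted power in these runs was 51–54%, so the power level depends heavily on the assumed rates.

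**The case against.** The strongest reply is that nothing here is wrong. A pre-specified two-proportion test is valid and transparent. Chance baseline imbalance is already allowed for in its error rate, and blocking balances the arms within each site. No section promises an adjusted remission analysis, so the protocol does not contradict itself. All of this stands, and it makes the point one of efficiency.

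A second reply is that the gain is unproven. The protocol does not show that remission depends on the starting score, the entry threshold narrows the baseline range, and at ρ = 0 the gain is nil. This also stands, which is why the range must begin at zero. The simulation also modelled HDRS-17 ≤7 only, not MADRS remission, and had no missing data.

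A reader might infer three stronger things that the documents do not support:
- **That ignoring the site strata is a material fault.** "done independently for the two sites" does make site a stratum, but stratifying by site alone recovers practically nothing, so a site-stratified Mantel–Haenszel analysis would not be a useful minimum.
- **That response needs the same change.** The named test sits with the remission definition, and no test is clearly fixed for response. Response is a percentage change from baseline, so the baseline score already enters it. In the runs of step 7 the variance ratio for response was about 1.00 at ρ = 0.1–0.3.
- **That the stand-alone power gain carries over in full to the trial.** Section 22.10 places two tests before remission and then applies Hochberg, so the gain in the chance of a remission claim is smaller.

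**Conclusion.** The point holds as a low-severity, low-cost improvement. Section 22.8 itself fixes an unadjusted remission test and leaves out a strong candidate covariate that is collected on everyone, together with the randomisation stratum. The test controls its error rate. Adjustment would reduce the variance of the remission difference by about 0% to 13% and add about 0 to 7 points of stand-alone power. This rests on 108 per arm, a 3.2-point effect, remission of about 20% against 33%, and a correlation of 0 to 0.5. The rates and the correlation are assumptions, so the protocol alone cannot place the gain within that range. Almost all of it comes from the baseline score.

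**What to change.** In Section 22.8, replace the remission test with a covariate-adjusted risk difference. Fit a logistic model on arm, site and the matching baseline score (HDRS-17 for HDRS-17 remission, MADRS for MADRS remission), standardise over the analysed sample, and test at the same one-sided level with a robust standard error. The estimand remains a difference in proportions. Keep the crude proportions and the Newcombe interval as the descriptive display. Make the change before unblinding, so that the choice of covariates cannot look data-driven, and carry the same wording into the SAP.

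The cost is one sentence and a few lines of code, with no new data. The downside is a slightly less simple test, and no gain if the baseline score turns out not to predict remission.

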11.7 EXPLORATORY ENDPOINTS

- Young Mania Rating Scale (YMRS) at 10 weeks.
- tDCS Adverse Events Questionnaire (AEQ) at 10 and 20 weeks
- Hamilton Anxiety Rating Scale (HAM-A) change at week 10.

- HDRS-17, MADRS, MADRS-s mean decrease, and remission and response rate at 20 weeks (after open-label) compared to open-label start and baseline.
- Correlation between MADRS and MADRS-s.
- Correlation between adherence to stimulation and HDRS-17/MADRS decrease in the active group at 10 weeks.
- Neuropsychological measure: verbal learning (Rey Auditory Verbal Learning Test (RAVLT) and information processing speed (Symbol-Digit Modalities Test (SDMT)
- Treatment acceptability questionnaire (TAQ) as developed by UEL. There is one form at baseline and another at week 10 and 20.
- The within-patient clinically meaningful improvement as defined as at least -3 points on the HDRS-17 scale. The percentage of subjects for each arm that reaches -3 points or more improvement and also the Cumulative Distribution Function Curves of Change in HDRS-17 Score from Baseline to Primary end-point by arm.

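### EQ-5D-3L defaults to an unadjusted comparison of change under protocol section 22.8; ANCOVA on the baseline score would be more precise and needs no new data

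*Protocol*

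**What the plan says.** EQ-5D-3L is a secondary endpoint in protocol section 11.6. Section 22.8 lists it as "Quality of life improvement as measured by EQ-5D-3L in the active compared to sham arm at week 10 compared to baseline", with no test, model or covariate attached.

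The same section sets the general treatment of secondary endpoints:

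- "Secondary effectiveness endpoints will be analyzed descriptively".
- For continuous variables, group differences, where specified, "will be summarized with the differences of the two means, and 95% confidence intervals for the difference between the means".
- "The confidence interval for the difference of two means will be calculated under the assumption of unequal variances".

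Two endpoints in the list are taken out of this rule. For MADRS change, "This will be evaluated using the same statistical methodology as the primary endpoint", which by section 22.5 means a mixed model for repeated measures. Remission gets a one-sided comparison of proportions.

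The list is introduced by "There are three secondary endpoints controlled multiplicity (see below" and then carries four bullets, of which EQ-5D-3L is the fourth. Section 22.10 tests clinical response after the primary endpoint and puts the remaining endpoints through Hochberg, with full details left to the SAP.

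EQ-5D-3L is taken at the baseline call (section 13.1) and at Week 10 (13.4), but is not listed for Weeks 1, 4 and 7 (13.3). Randomisation is "done independently for the two sites" (section 22.4). Among the exploratory endpoints, section 11.7 has "Hamilton Anxiety Rating Scale (HAM-A) change at week 10", and section 22.9 tags HAM-A as continuous, so the same general rule reaches it.

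**The concern.** Every randomised participant should have a baseline EQ-5D-3L score, but the rule that applies by default uses it only by subtraction. A raw change score puts a fixed weight of one on baseline. When baseline and Week 10 are imperfectly correlated and equally variable, that weight is too large and adds noise to the comparison. ANCOVA estimates the weight from the data.

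What is at stake is the width of the EQ-5D-3L interval and, if the endpoint is formally tested, its power. A chance baseline imbalance also carries into the realised raw-change estimate, whereas ANCOVA corrects for it. Site, within which randomisation is blocked, is likewise absent from the default comparison. The plan is uneven as well: the primary endpoint and MADRS change are adjusted, while EQ-5D-3L in the same list is not.

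**Working it through.** **1. The plan's own figures.** The protocol gives no effect, SD, correlation or power for EQ-5D-3L. Its only power calculation is for HDRS-17 (section 22.2): difference 3.2, SDs 7.1 and 7.9, one-sided 0.025, 80% power.

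- Common SD = sqrt((7.1² + 7.9²)/2) = sqrt(56.41) = 7.51.
- Normal approximation: n per arm = 2 × (0.8416 + 1.9600)² × 56.41 / 3.2² = 86.5, so 87 per arm or 174 in total. With the t distribution, power is 79.8% at 174 and 80.2% at 176, which reproduces the stated 176.
- At 216 subjects the t-test has 87.6% power, as stated. 216/0.80 = 270, as stated.

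These figures are sound. The 80% and 87.6% are borrowed below only as illustrative starting points for EQ-5D-3L.

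**2. Variance of the two estimators.** Let the baseline and Week 10 scores both have variance s² within arm, and let rho be their correlation (assumed).

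- Raw change: s² + s² − 2·rho·s² = 2s²(1 − rho).
- ANCOVA: s²(1 − rho²) = s²(1 − rho)(1 + rho).
- Ratio of ANCOVA to raw change: (1 + rho)/2, which is below 1 for every rho below 1.

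If the variances differ (s0² at baseline, s1² at Week 10), raw change minus ANCOVA is s0² + s1² − 2·rho·s0·s1 − s1²(1 − rho²) = (s0 − rho·s1)². This is never negative, so in large samples adjustment cannot lose, although the size of the gain then differs from (1 + rho)/2.

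**3. Interval width.** Relative width is sqrt((1 + rho)/2): 0.806, 0.866 and 0.922 at rho 0.3, 0.5 and 0.7. The interval is about 19%, 13% or 8% narrower. This applies even if EQ-5D-3L is only reported descriptively.

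**4. Power, if tested at one-sided 0.025.** ANCOVA power = Phi((z_base + 1.960)/sqrt((1 + rho)/2) − 1.960), with z_base = 0.842 for 80% and 1.155 for 87.6%. Example at rho 0.5 from 80%: 2.802/0.866 − 1.960 = 1.275, so 89.9%.

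| rho | ratio | from 80% | gain (points) | from 87.6% | gain (points) |
|---|---|---|---|---|---|
| 0.3 | 0.65 | 93.5% | 13.5 | 97.2% | 9.6 |
| 0.5 | 0.75 | 89.9% | 9.9 | 94.9% | 7.3 |
| 0.7 | 0.85 | 86.0% | 6.0 | 92.2% | 4.6 |
| 0.9 | 0.95 | 82.0% | 2.0 | 89.2% | 1.6 |

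**5. Simulation check.** With 108 per arm, 4,000 runs and the effect set for 80% raw-change power, the Welch test on change gave 79.7%, 79.5% and 80.2% at rho 0.3, 0.5 and 0.7. ANCOVA gave 93.0%, 89.4% and 85.3%. The formula holds at this sample size. Site was not modelled, so no gain is claimed for it.

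**The case against.** The strongest objection is that the protocol never says EQ-5D-3L will be analysed as an unadjusted change. The general paragraph is a rule for summaries, it covers group differences only where specified, and EQ-5D-3L carries no continuous-variable tag. Clinical response, in the same list, also has no named test. Reference to baseline does not by itself fix a raw change score, since the primary endpoint is worded in a similar way and is analysed by an adjusted model. The SAP, which is not at hand, may assign one here too.

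Part of this stands: the unadjusted analysis is inferred from the general rule and is not stated for EQ-5D-3L. But section 22.8 does more than stay silent. It states an estimator for continuous secondary variables and exempts MADRS change by name. Unlike sections 22.5.1, 22.6 and 22.10, it does not refer the method to the SAP. A SAP that used ANCOVA would depart from this text, so the wording needs attention either way.

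Three stronger readings are tempting and are not supported:

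- A reader might infer that EQ-5D-3L, listed last, faces the strictest threshold. Hochberg is a step-up procedure without a fixed order. The threshold depends on the rank of the p-value, and the largest p-value is compared with the full 0.025. It is not even settled that EQ-5D-3L belongs to the family.
- A reader might take a loss of 6 to 14 points as a property of this trial. It holds only for an assumed 80% base, equal variances and rho from 0.7 to 0.3.
- A reader might infer bias or an inflated type I error. Under randomisation the unadjusted difference is unbiased on average and its type I error is unaffected.

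**Conclusion.** The point holds as one of precision. The only method in the protocol that can cover EQ-5D-3L is an unadjusted comparison of change, although the baseline score is collected and MADRS change beside it is adjusted. With equal variances and rho between 0.3 and 0.7, both assumptions, the unadjusted interval is wider than it need be. The power given up is about 6 to 14 points from an 80% base and about 5 to 10 points from an 87.6% base. At rho 0.9 from an 80% base it is about 2 points. The direction does not depend on these assumptions; the size does. The primary conclusion and the sample size are untouched.

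A separate inconsistency must be resolved with it: three controlled endpoints are announced and four are listed, so it is unclear whether the power figures bear on a formal test or only the interval width matters. For HAM-A, which is exploratory and outside the testing order, the gain is in precision only.

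**What to change.** - In section 22.8, state that EQ-5D-3L at Week 10 is compared between arms by ANCOVA with treatment, site and baseline EQ-5D-3L, reporting the adjusted mean difference, its 95% confidence interval and the one-sided p-value. With a single blinded post-baseline value, a repeated-measures model is not needed. Keep raw means and SDs by arm as descriptive output.
- Reconcile the announced count of three controlled endpoints with the four listed, and say in sections 22.8 and 22.10 whether EQ-5D-3L enters the Hochberg family.
- Optionally, use the same model with baseline HAM-A for the exploratory HAM-A change.
- Carry the same wording into the SAP, before any comparative data are seen, including at the interim analysis of section 22.15.

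The cost is protocol and SAP wording and one additional model per endpoint. No new data, visits or participants are needed.
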